**Table 1. Schedule of study events.**

	Pre-enrollment	Initial Visit	Second in Person Visit	Phone Sessions (12 weeks)	Follow-up Phone Call (Week 12)	Follow-up Phone Call (Week 24)
Cognitive screen	X					

Chart review to confirm eligibility	X					
Assessment of inclusion criteria (MOS, NYHA class)	X					
Chart review for baseline characteristics		X				
Randomization to PP or Control Condition			X			
Weekly intervention exercises*			X	X		
Exercise ratings			X	X		
Self-report measures (SSQ, SRMA, MOS, LOT-R, PANAS, HADS, KCCQ, SF-12, SOM)		X			X	X
Objective adherence data (ActiGraph step counter)		X			X	X
Satisfaction with Care					X	X
Hospital Readmissions					X	X

\*Type of exercise assigned will depend on whether participant is in PP-MI or control condition

## B. Drugs to be used

No specific medications are being studied or administered solely for research purposes in this study.

## C. Devices to be used

No specific devices are being studied or administered solely for research purposes in this study.

## D. Procedures/ surgical interventions

No procedures or surgical interventions will be performed solely for research purposes in this study.

## E. Data to be collected (See Table 1)

**Baseline Data:** Participants will complete the MOS, SSQ, SOM, LOT-R, PANAS, HADS, KCCQ, SRMA, and SF-12 in person and will receive an Actigraph accelerometer. They will be asked to begin wearing the accelerometer after their initial visit and prior to in-person visit #2 to measure their baseline physical activity.

Baseline information about enrolled participants will also be obtained from the participants, care providers, and electronic medical record as required for characterization of our population. This information will include data regarding medical history (history of coronary artery disease, acute coronary syndrome, coronary artery bypass graft, hypertension, diabetes mellitus, hyperlipidemia, body mass index, height, weight, and current smoking), current medical variables (renal function, N-terminal pro-B-type natriuretic peptide, left ventricular ejection fraction, NYHA class), medications, and sociodemographic data (age, gender,

race/ethnicity, living alone, education). This information will help us to ensure that the population we recruit is a representative population of patients suffering from HF so that the health behavior intervention we are testing is applicable to the broadest population of patients.

**Feasibility (primary study aim):** Feasibility will be measured by the number of PP sessions that were completed by participants. We will consider the intervention feasible if the majority of participants complete at least 7 of 12 exercises/sessions.

**Acceptability:** Following each PP exercise, participants will be asked to rate the ease of completion and subjective helpfulness of the exercise on a scale of 0 (very difficult/not helpful) to 10 (very easy/very helpful).

**Immediate impact:** To examine the immediate impact of the PP exercises on positive affect and optimism, participants will be asked to rate these psychological states before and after each exercise on a 10-point Likert scale (0 = not happy/optimistic, 10 = very happy/optimistic).

**Measurement of health behaviors.** We will assess three main health behaviors in this trial.

**(a) Physical activity (primary health behavior outcome measure).** We selected physical activity as our main health behavior outcome for several reasons. Physical activity is a key modifiable prognostic factor in HF patients and has been associated with improved exercise capacity, QoL, and survival in this population. Furthermore, there are established links between higher levels of positive emotions (particularly optimism) and increased physical activity, suggesting that a PP intervention could impact this behavior. Finally, increasing physical activity is likely to require a relatively broad approach, as compared to other behaviors, which may improve with simple interventions such as electronic reminders.

Physical activity will be measured using the ActiGraph GT3X+ three-axis accelerometer (ActiGraph, LLC, Pensacola, FL). Accelerometers are often considered to be the standard for measuring habitual physical activity. ActiGraph GT3X+ step counters are validated as measures of physical activity and have been used in numerous studies of physical activity in patients with medical illness. We chose to use ActiGraph GT3X+ accelerometers because they are the most widely used monitors for research purposes and adequately discriminate between different levels of activity. In this trial, participants will wear the accelerometer (for 1 week at baseline and 1 week at each follow-up time point) to assess the feasibility of doing so, ensure adequate capture of physical activity, and examine the impact of the intervention on this health behavior. We will measure the number of steps taken daily and the amount of time spent in moderate to vigorous physical activity (MVPA) to examine the impact of the intervention on these important outcomes. We will turn off all notifications on the device prior to the start of the study. We will require at least 480 minutes of wear time to be considered a valid day, and at least 5 valid days for a participant's data to be considered complete. If a participant does not provide at least this much data, we will ask the participant to re-wear the step counter until information from at least 5 valid days has been captured.

**(b) Medication adherence.** We will assess medication adherence using a self-report medication adherence (SRMA) measure. Specifically, we will ask participants what percent of the time (in 10% increments) they took all of their medications as prescribed in the past week

and in the past 2 weeks. These questions were adapted from the adherence measure used in the Heart and Soul Study.

**(c) Dietary adherence.** We will assess sodium intake over the past month using the Scored Sodium Questionnaire (SSQ). This scale assesses the frequency with which participants consume a variety of sodium-containing foods, ranging from “Rarely or Never Eaten” to “At Least Once Daily.” Total SSQ score has been shown to correlate significantly with 24-hour urinary sodium, and the SSQ has been validated in patients with significant medical illness. If participants are hospitalized, they will be asked to describe their sodium intake prior to admission, given that their diet in the hospital may be significantly different than their typical diet at home. The SSQ will be completed both at baseline and again at the 12 and 24-week follow ups.

**(d) Self-reported adherence.** We will assess self-reported adherence using the MOS items regarding diet/exercise/medications. Participants will be asked to rate how often they completed each health behavior over the last month, with choices rating from “none of the time” to “all of the time.” The MOS has been used in multiple prior studies assessing adherence in cardiac patients, including our own studies in this population.

**Measurement of psychological outcomes.** We will measure optimism, positive affect and other psychological constructs that may potentially be impacted by the PP-based health behavior intervention that will be tested in subsequent trials. Doing so in this study will allow us to evaluate the feasibility of using these scales in this specific patient population.

**(a) Optimism** will be measured using the Life Orientation Test-Revised (LOT-R), a well-validated 6-item instrument, and the State Optimism Measure (SOM). Dispositional optimism is the positive psychological state most linked to cardiac outcomes, and the LOT-R has been used to measure optimism in many studies of cardiac patients. Though dispositional optimism theoretically would be stable over time, research suggests that LOT-R scores can change quickly in response to psychological interventions. We also will be using a short scale developed by our team (SOM) to measure state optimism.

**(b) Positive affect** (primary psychological outcome measure) will be measured using the positive affect items on the Positive and Negative Affect Schedule (PANAS), a well-validated scale used in other intervention trials and in patients with HF.

**(c) Anxiety and depression** will be measured using the anxiety and depression subscales of the Hospital Anxiety and Depression Scale (HADS). This well-validated scale has been used in many studies of patients with heart disease (including our group’s studies), and has the advantage of having few somatic symptom items that can confound mood/anxiety assessment in medically-ill patients.

**Measurement of physical outcomes.** We will also assess selected physical outcomes.

**(a) Cardiac symptoms and HF-related QoL** (primary functional outcome measure) will be measured with the Kansas City Cardiomyopathy Questionnaire (KCCQ), a well-validated questionnaire of health status in HF. The full scale will be used to measure HF-specific health-related QoL (HRQoL), and an eight-question subset of the KCCQ will be used as a measure of HF symptoms. The KCCQ is a valid, reliable, and responsive instrument in patients with HF and is strongly correlated with NYHA class. We chose the KCCQ as our primary functional

outcome measure because it likely would be affected by all three of our health behaviors of interest (physical activity, medication adherence, and diet).

**(b) Generic HRQoL** will be assessed via the Medical Outcomes Study Short Form-12 (SF-12), an instrument which has been used in multiple cardiac studies in the past, including our work. The SF-12 also is a reliable marker of QoL in HF and has been associated with mortality in this high-risk cohort.

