## **V. STUDY PROCEDURES**

#### **A. Study visits/evaluations (See Table 1)**

**Initial visit (Week 1; in person).** The initial visit will occur in an MGH inpatient unit (for those recruited inpatient), in an office on the MGH main campus (for those recruited via opt-out letter), or over the phone (if a participant prefers to not come to the hospital for an in-person visit). Height and weight will be recorded (measured in person or taken from the medical record if inpatient). Participants then will meet with a member of the study staff (the study “trainer”) and complete self-report questionnaires. These questionnaires assess state optimism (State Optimism Measure; SOM), general optimism (Life Orientation Test-Revised; LOT-R), anxiety/depression (Hospital Anxiety and Depression Scale; HADS), positive emotions (Positive and Negative Affect Schedule; PANAS), HRQoL (Medical Outcomes Study; MOS, Short Form-12; SF-12), cardiac symptoms and heart failure-related QoL (Kansas City Cardiomyopathy Questionnaire; KCCQ), medication adherence (Self-Reported Medication Adherence [adapted from the Heart and Soul Study]; SRMA), and sodium intake (Scored Sodium Questionnaire; SSQ). Participants will also answer questions about their alcohol (using the AUDIT-C) and cigarette use. In sum, these scales should take approximately 30 minutes to complete.

After completing the baseline questionnaires, participants will receive an Actigraph GT3X+ accelerometer, and its use will be demonstrated by the trainer. We will measure activity at baseline (for 7 days) and in the 7 days following the 12 and 24-week assessments (we will send participants the ActiGraph in the mail at the appropriate time). In contrast to the pedometer, which is used by participants to monitor their activity, the ActiGraph accelerometer provides no information to participants about their physical activity and will only be used by the study team to measure physical activity as an outcome.

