ActiGraph accelerometers are validated as measures of physical activity and have been used in numerous studies of physical activity in patients with medical illness. The accelerometer is a small 1.5” square device that can be worn on an elastic band (around the lower waist) or clipped onto a belt. It tracks the number of steps taken. After explaining how to use the accelerometer, the study trainer will schedule a time for the participant to come in for the second in person visit one week after the initial visit. In total this initial visit will take approximately 45 minutes.

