#### **Second Visit (Week 2; in person).**

At the second in person visit, which will take place one week after the initial visit, we will collect the Actigraph from participants, and check to ensure participants had at least 5 valid days of data. At this point, participants will be randomized to one of the three conditions noted above. Patients in the TAU group will receive no further intervention and will be scheduled for a follow-up appointment in 12 weeks. Participants in the PP and goal-setting or MI-only conditions will be provided with a manual corresponding to their treatment condition, as well as a copy of *Learning to Live with Heart Failure*, a practical guide which is provided by MGH to all HF patients admitted to a cardiology unit at MGH.

**PP and goal-setting intervention:** The trainer then will introduce the participant to the PP and goal-setting portions of the intervention. For the PP portion, participants will be assigned the first exercise (Gratitude for Positive Events) and will be instructed to perform the exercise within the next week. Prior to completing the exercise, participants will be asked to rate their current level of happiness and optimism, using a 10-point Likert scale. Immediately after completing the

exercise, participants will rate the ease of exercise completion, overall utility of the exercise, and their current levels of happiness and optimism, all using 10-point Likert scales. For the first goal-setting session, the trainer will discuss the importance of physical activity in HF. Participants will be given a pedometer, which participants will use to monitor the number of steps they take daily over the following week. The trainer will instruct them in its use and set a goal for monitoring their baseline physical activity over the next week. This pedometer will not be used as an outcome measure but simply will be a tool that participants can use to monitor their activity.

*MI-based educational intervention:* Participants in the MI-only control group will similarly have the rationale of the MI-based health behavior program explained to them, and will be assigned the first exercise. They also will be given a pedometer for their personal use. We estimate that this portion of the visit will take approximately 20 minutes.

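### Inpatient recruits: ward days can count in the baseline step week, so a within-arm pre-post gain in steps can be inflated; planned between-arm comparisons are not biased

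*Combined protocol and SAP*

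**What the plan says.** Section V.A places the first contact for these patients in hospital: "The initial visit will occur in an MGH inpatient unit (for those recruited inpatient"). They complete the questionnaires and receive the ActiGraph there. The trainer will then "schedule a time for the participant to come in for the second in person visit one week after the initial visit". The Second Visit paragraph repeats the timing: "At the second in person visit, which will take place one week after the initial visit, we will collect the Actigraph from participants". Under Section IV.C, randomization follows once those data are found adequate.

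Section V.E gives the start of wear as "They will be asked to begin wearing the accelerometer after their initial visit and prior to in-person visit #2". The test of a valid day is duration: "We will require at least 480 minutes of wear time to be considered a valid day". Five valid days are needed, and if there are fewer, "we will ask the participant to re-wear the step counter until information from at least 5 valid days has been captured".

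For sodium intake, Section V.E(c) deals with hospital stay directly: "If participants are hospitalized, they will be asked to describe their sodium intake prior to admission". Its reason is that hospital diet may differ from diet at home. No such rule appears for steps, for medication adherence ("we will ask participants what percent of the time (in 10% increments) they took all of their medications as prescribed in the past week", and also over the past 2 weeks), or for the MOS items, which cover the last month.

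The Aim 3 hypothesis in Section II predicts significant pre-post improvement in adherence and functional outcomes with the intervention. Section VI.C compares steps between groups at 12 and 24 weeks by rank sum test.

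**The concern.** Section V.E(a) justifies the accelerometer as a standard for habitual activity. Steps taken on a ward are not habitual and would probably be fewer than at home. If some inpatient recruits contribute ward days at baseline and wear the device at home 12 and 24 weeks later, their steps rise even if the intervention does nothing. Randomization does not protect a comparison of an arm with its own baseline. Section VI.D says the pilot is not designed to detect between-group differences in health behavior outcomes, so readers may lean on pre-post change. The protocol accepts the reasoning for sodium but does not apply it to its primary health behavior outcome.

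**Working it through.** **1. Can ward days enter the baseline as written?** The interval from the initial visit to Visit 2 is one week, and planned wear is 7 days. The full week fits only if wear starts more or less at once. With 5 valid days required, the start can slip by at most 7 − 5 = 2 days before re-wear is triggered. A patient who stays on the ward after the initial visit and follows the schedule therefore wears the device there. Those days count if wear reaches 480 minutes.

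**2. Which comparisons are affected?**
- Between-arm steps (VI.C): the rank sum test uses 12- and 24-week values, so baseline does not enter.
- Between-arm change (VI.A and B, VI.C): baseline wear is finished and checked before assignment, so any ward-day artifact is equal across arms in expectation. In a simulated check (30 of 60 inpatients, two arms of 20, t test on change, no true effect), type I error was 0.048 and 0.049 at the two settings tried. Chance imbalance in inpatient share adds noise only: the SD of the difference is √(2s(1−s)/20) = 0.14 at s = 25% and 0.16 at s = 50%.
- Within-arm pre-post change (Aim 3 hypothesis): exposed.
- Feasibility: based on sessions completed, so untouched.

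**3. How large could it be?** The plan has no figure to reproduce here. All four inputs below are assumptions:
- s, inpatient share: 10–50%
- k, ward days among the 7: 1–3
- D, ward deficit: 1,000–2,000 steps/day
- SD of change: 1,500–2,500

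False arm-level gain = s × D × k/7. The last column is the chance of a significant gain with no true effect, from a simulated one-sample t test with n = 20 and two-sided 0.05 (2.5% without distortion).

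| s | k | D | SD | False gain (steps/day) | Chance |
|---|---|---|---|---|---|
| 10% | 1 | 1,000 | 2,500 | 0.10 × 1,000 × 1/7 = 14 | 2.6% |
| 25% | 2 | 1,000–2,000 | 1,500–2,500 | 0.25 × D × 2/7 = 71–143 | 3.3–5.9% |
| 50% | 3 | 2,000 | 1,500 | 0.50 × 2,000 × 3/7 = 429 | 21.4% |

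The last row needs every input at its extreme. The test column is illustrative only: Section VI.C names no within-arm step test and expects steps to be skewed.

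In relative terms, let h be ward steps divided by home steps. The apparent rise with no true change is 1/(1 − s(k/7)(1 − h)) − 1. With h = 0.5 and k = 2, this is 16.7% for one inpatient (s = 1), 7.7% for an arm at s = 50%, and 3.7% at s = 25%.

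**4. Medication recall.** With assumed home adherence of 80% and 100% on 3 hospital days, the past-week answer rises by 3 × 20/7 = 8.6 points and the past-2-weeks answer by 3 × 20/14 = 4.3. Both are less than one 10% response step. The direction is opposite to that for steps: a raised baseline hides a gain.

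**The case against.** The strongest reply is that no named analysis is harmed. Section VI.C contains only between-arm comparisons for Aim 3, the primary aim is feasibility, and what remains is one hypothesis sentence. That stands, and it limits the weight of the point. A reader might infer that the trial's step comparison between arms is biased in favor of the intervention. The documents do not support that, for the reasons in step 2 of the working.

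A reader might also infer that ward days will be common or the distortion large. The documents do not show this either. Being scheduled to come in a week later suggests discharge by then, although Section IV.C calls Visit 2 an in-hospital visit. The wording on start of wear gives a window, which a patient discharged the same day could meet entirely at home. Hospital days during follow-up wear could also offset part of the effect, since readmissions are expected enough to be asked about. None of this closes the gap, because neither passage sets when wear starts.

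Finally, it is tempting to require pre-admission recall for medication adherence and the MOS, as for sodium. Recall anchored to the period before an admission is open to regression to the mean. It could replace a bias that hides a gain with one that shows a false gain. That objection holds, so re-anchoring should not be a main recommendation. The MOS gap is nonetheless real: Table 1 lists the MOS at the initial visit as a self-report measure, separately from its use for eligibility.

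**Conclusion.** The point holds as a limited design weakness. Following the schedule and valid-day rule as written can put ward days into baseline steps for inpatient recruits, and this would probably inflate within-arm pre-post change. Two assumptions carry that conclusion: some inpatient recruits stay on the ward after the initial visit, and they walk less there than at home. Its size cannot be determined from the documents. It is negligible with few inpatients and short remaining stays, and becomes material only with many inpatients and about three ward days each. It deserves correction because correction is cheap, with low-to-moderate weight and medium confidence. The stated power and sample size are unaffected.

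**What to change.** 1. In Sections V.A and V.E, for inpatient recruits, start the 7-day baseline wear after discharge and time Visit 2 one week after that start. Alternatively, record the discharge date, exclude ward days from valid days, and apply the existing re-wear rule to reach 5. Of 7 worn days, up to 2 ward days still leave 5 if the rest are valid (7 − 2 = 5); 3 or more trigger re-wear.
2. Report within-arm step change by recruitment setting, as description, and rest Aim 3 conclusions on the between-group comparisons already planned.
3. For SRMA and the baseline MOS outcome items, at minimum record whether the recall window includes hospital days, and interpret within-arm change with that caveat. Re-anchoring the recall is optional.

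The cost is a few sentences and one or two recorded items. For inpatients, the interval to randomization lengthens somewhat. Re-wear may add one contact, because assignment waits for adequate data. Some extra drop-out is possible at a stage where Section VI.D already allows for losing 75 − 60 = 15 participants. Early post-discharge recovery would remain in the baseline, and hospital days during follow-up wear are not addressed, which is why item 2 is needed as well.

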## VI. BIOSTATISTICAL ANALYSIS

### A and B. Specific data variables and study endpoints

**Aim #1** (*Feasibility [primary outcome]*, acceptability, and immediate impact): To assess whether PP exercises administered over the phone are feasible, acceptable, and lead to improvements in positive affect and optimism in patients with NYHA class I-III HF.

